The results for the primary hypothesis will be analyzed by means of a one-sided 95% confidence interval on the difference in proportion of participants with one or more gout flare events. The test of the difference between proportions will have one-sided type I error of 5%. Starting with a total of 950 participants, allowing 5% dropout, and retaining 900 participants, the test has 90% power to reject the null hypothesis of inferiority with a total of 900 participants, 450 participants per arm,

For large samples, regarding the difference between proportions as the difference between means, the use of the standard Student's t distribution closely approximates the non-central t-distribution and justifies use of the power formula 3.2.4 (in section 3.2.2) below (Chow, Shao, and Wang (86):

$$n = n_1 = n_2 = \frac{(Z_\alpha + Z_\beta)^2 2\sigma^2}{(D - B)^2}$$

Note: $n = 450$ is the number of participants in each of the two study arms, $Z_\alpha = 1.645$ is the cut point for a one-sided test with a 5%, Type I error, $Z_\beta = 1.28$ provides 90% power, Bound = 8%, $D=0\%$ is the true difference between the treatment outcome measures, and $\sigma^2 = 0.16$ is the variance associated with the distribution of for a single Bernoulli observation.

As rates are uncertain, we note that if the Phase 3 rate of gout flares is either 15%, 20%, or 25% then the respective statistical powers are 96%, 91%, and 87%. With a rate of 20%, but a higher dropout rate of 10%, the power is 90%. Non-adherence to treatment, inability to attain $sUA < 6$ mg/dl, or failure to appear for clinic visits will not affect dropout, only the explicit decision of the patient to leave the study. Participants who experience toxicity that either reduced dosage or other medications reduce to a tolerable level can remain on study if they wish to do so.

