¶ Hyperechoic irregular enhancement over the surface of the hyaline cartilage that is independent of the insonation angle of the ultrasound beam (note: false positive DCS (artifact) may appear at the cartilage surface that should disappear with a change in the insonation angle of the probe).^{31,32}

§Presence of color-coded urate at articular or peri-articular sites. Images should be acquired using a dual energy computed tomography scanner, with data acquired at 80 and 140 kV and analyzed using gout-specific software with a two material decomposition algorithm which color-codes urate.³³ A positive scan is defined as the presence of color-coded urate at articular or peri-articular sites. Nailbed, submillimeter, skin, motion, beam hardening and vascular artefacts should not be interpreted as evidence of DECT urate deposition.³⁴

**Erosion is defined as a cortical break with sclerotic margin and overhanging edge; excluding DIP joints and gull wing appearance.

Participant ID _____

LSI/Sub I Name: _____ LSI/Sub-I Signature _____ Date: _____

The study will include gout patients not only receiving first-time ULT but will also allow for the inclusion of gout patients who remain hyperuricemic (serum urate ≥ 6.8 mg/dl) despite ongoing therapy with uricosurics (e.g. probenecid) or allopurinol at daily doses ≤ 300 mg. Uricosurics will require a 14-day wash-out prior to study enrollment. Because febuxostat is non-formulary in the VA and considered only for patients failing or intolerant to allopurinol, patients with prior use of this agent will be excluded from study participation.

Inclusion Criteria:

1. Age ≥ 18 years
2. History of gout – crystal proven or historical as defined by ACR criteria listed above
3. Serum urate level ≥ 6.8 mg/dl

Exclusion Criteria:

1. Stage 4 or 5 Chronic Kidney Disease (CKD) – defined as eGFR of <30 ml/min/1.73 m²
2. Women younger than 50 years of age
3. Patients with a history of prior solid organ / hematopoietic transplantation
4. Previous allergy or intolerance to allopurinol
5. Patients who are not candidates for any of the recommended prophylactic medications (colchicine, naproxen or glucocorticoids)
6. Patients who in the opinion of the investigator have a high genetic risk for allopurinol hypersensitivity syndrome (AHS*) unless they have been found to be negative for HLA B5801.
7. Previous history of failure to reach target uric acid levels despite therapy with allopurinol at dose > 300 mg/day
8. Prior febuxostat use

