Gout patients who remain hyperuricemic (sUA ≥ 6.8 mg/dl) despite ongoing allopurinol use in daily doses ≤ 300 mg will be allowed to enroll in the study. These patients will be randomized to receive febuxostat or to remain on allopurinol. For those initiating febuxostat, the starting dose will be 40 mg daily irrespective of prior allopurinol dose. For pre-study allopurinol users randomized to the allopurinol treatment arm, patients will continue with their current dose until scheduled for dose escalation based on the above schedule. For example, a patient on allopurinol 300 mg daily randomized to the allopurinol treatment arm would remain on 300 mg until week 9 of the study at which time they would be eligible for dose escalation. For a similar patient taking allopurinol 200 mg daily, the first possible titration will occur at week 6. We have opted for this approach to minimize the risks of gout flares that may occur as a consequence of sUA fluctuations and to ensure the same intensity of follow-up for all participants.

Recognizing that true equivalency doses have never been established for allopurinol and febuxostat, the dose titration schedule has been generated in order to yield a similar 'velocity' in sUA reduction in the two treatment arms over the first 24 weeks of the study. We have opted for the proposed dosing schedule for febuxostat, recognizing that the drug's package insert recommends starting all patients on 40 mg/day with a dose titration to 80 mg/day after 2 weeks for those with sUA ≥ 6.0 mg/dl (≥5.0 mg/dl if

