As outlined above in Section VII, patients reporting the occurrence of a new rash (outside the context of the ULT clinic visit), will be asked to present for an in-person evaluation by a study investigator. Structured data will be collected for each rash reported.

After each sUA draw, study personnel will contact the patient (in-person for ULT clinic visits; by telephone for blood draws not coinciding with visit) and adjust the study medication as described above to reach target sUA levels. Information pertinent to adverse events will be collected every 3 weeks for all study participants during Phase 1 (0 to 24 weeks) either at the time of ULT clinic or during telephone encounters. During Phase 2 of the study (24 to 48 weeks), adverse event information will be collected every 6 weeks during ULT clinic visits. For additional information about adverse event surveillance, see Section XVI. Increased surveillance frequency scheduled during Phase 1 of the study is predicated on data demonstrating that serious adverse events (particularly serious dermatologic adverse events related to allopurinol) are most common during this early period of drug initiation. As part of a recent retrospective case-control study, investigators observed that 90% of allopurinol hypersensitivity syndrome (AHS) occurs in the first 6-months of treatment (59).

Post Study Care:

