### **5.2. Balancing During Randomization**

Simple randomization will be used to ensure that equal proportions of participants with the following characteristics are in the two treatment arms:

- 1) CKD Stage 3;
- 2) marked hyperuricemia defined as a sUA  $\geq$  9.0 mg/dl;
- 3) presence of tophi (focused examination involving the hands, elbows, feet, and ears, which are the most common sites for tophaceous deposits); and
- 4) participants with current receipt of allopurinol.

Furthermore, to guarantee enrollment of a sufficient number of gout participants with CKD stage 3 (eGFR  $\geq 30$  but  $< 60$  ml/min/1.73 m^2) to address a key secondary objective (see Section 2), we will randomize at least one participant with CKD Stage 3 for every two participants with preserved renal function (eGFR  $\geq 60$  ml/min/1.73 m^2).

Distribution of all these variables across the treatment groups will be closely monitored throughout the study. If any unbalancing happens on one or more characteristics listed above, a biased coin algorithm will be implemented to remedy the condition.

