  - a. We will model the number of gout flares, which can have substantial variation, as Poisson random variables. We will use Poisson regression to compare treatments using a longitudinal repeated measure (PROC GLIMMIX and GENMOD in SAS). Missing data methods will address potential censoring of events among patients who appear to fail to report flares.
  - b. Flare counts will be analyzed separately during Phases 1, 2, and 3 because dose titration during Phase 1 tends to increase the counts, and this effect may still persist in Phase 2, particularly for those still undergoing dose titration; participants are expected to be in steady-state by Phase 3.
  - c. Phase 2 analysis will consider prophylactic treatment after a gout flare and severe side effects of treatment as predictors of subsequent counts.
  - d. During Phase 3 the same set of factors as well as Phase 2 counts will be used to predict gout flare counts. These time-dependent associations will require a mixed effects model using an auto correlated AR(1) variance-covariance to model the series of events.
  - e. For these analyses we may treat the counts as continuous measures in order to introduce more subtle variance-covariance structure and a variety of random effects.
- 7) To determine the patterns of tolerability/toxicity for each treatment during Phase 3 and then overall from weeks 1-72.
  - a. Toxicity events include rises in sUA levels, adverse changes in serum creatinine, CBC, liver function tests (LFTs), blood pressure, and the incidence of skin rashes. The incidence of cardiovascular events of interest will also be included in this analysis.
  - b. Within each Phase we will determine if the incidence of such events differs between treatments. In the Phase 3 analysis baseline covariates will include the summary of toxicity events during Phases 1 and 2 as well as the week 48 sUA level. As in the sixth secondary analysis the same statistical methods for Poisson counts will be used.
  - c. At each clinic visit we will assess the count of each type of major side effect episodes between visits. The analyses will compare treatments using a longitudinal repeated measures analysis with Poisson count, negative binomial counts, and binary outcomes

(PROC GLIMMAX and GENMOD in SAS). Missing data methods will address potential censoring of events among patients who fail to attend clinic visits.

- 8) To describe the effects of baseline covariates and time-dependent covariates on the primary results.

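### Tolerability results pool patients continuing allopurinol with patients starting it, and would tend to understate allopurinol's early intolerance in new starters

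*Protocol*

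**What the plan says.** Protocol section IX admits patients receiving urate-lowering therapy for the first time, and also patients who remain at or above 6.8 mg/dl on allopurinol at up to 300 mg/day. It excludes anyone with "Previous allergy or intolerance to allopurinol" and, separately, anyone who has used febuxostat before.

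Section X (Dosing of study medications) sets out how current users are handled: "For pre-study allopurinol users randomized to the allopurinol treatment arm, patients will continue with their current dose until scheduled for dose escalation". Its example is a 300 mg user who stays on that dose until week 9. A current user allocated to febuxostat begins at 40 mg, whatever the earlier allopurinol dose.

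Section XI supports the closer surveillance in Phase 1 with a case-control study in which "investigators observed that 90% of allopurinol hypersensitivity syndrome (AHS) occurs in the first 6-months of treatment".

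On the analysis, SAP 5.5 objective 7 says: "Within each Phase we will determine if the incidence of such events differs between treatments". Objective 1(b) compares adverse events, serious adverse events and related withdrawal between arms in CKD 3, and objective 6 compares flare counts by phase. SAP 3.7 tabulates adverse events by intervention group. None of these is split by allopurinol use at entry. SAP 5.2 balances the arms on "participants with current receipt of allopurinol", whereas the Randomization paragraph of protocol section VI balances on earlier receipt of any urate-lowering therapy.

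**The concern.** The two arms differ in more than the drug. Among patients already taking allopurinol, one arm stays on a drug it has so far tolerated and the other arm starts something new. Among everyone else, both arms start. The pooled tolerability comparison averages these two contrasts. In the first of them, allopurinol gains from prior selection: patients who reacted to it were kept out, and the continuing users may be past much of the period in which the protocol says hypersensitivity arises. No febuxostat patient can have that advantage.

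Tolerability is not a side issue here. The provider and patient surveys in protocol section III rank it second after flares. Section IV reports that about one provider in five believed febuxostat was better tolerated, a view the protocol treats as unsupported. A pooled finding of similar tolerability would be read as settling that question for a patient about to start treatment, when part of the allopurinol arm was not starting.

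**Working it through.** **The plan's own figure.** The documents give no figure for the tolerability comparisons. Their power statement concerns the primary test: "retaining 900 participants, the test has 90% power to reject the null hypothesis of inferiority". It reproduces. The formula gives n = (1.645 + 1.28)² × 2 × 0.16 / 0.08² = 427.8 per arm. Power at 450 per arm and a 20% flare rate is Φ(0.08/√(2 × 0.2 × 0.8/450) − 1.645) = Φ(1.355) = 91.2%, against 91% stated. Entry use plays no part in that calculation, so it neither supports nor weakens this point.

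**Who is established on the assigned drug.**

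| At entry | Allopurinol arm | Febuxostat arm |
|---|---|---|
| Not taking allopurinol | starts | starts |
| Taking allopurinol, up to 300 mg | continues | starts |

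Balancing makes the share of users equal across arms. It does not change the second row. A covariate-adjusted model with only a main effect for entry use still estimates one averaged treatment effect. Recovering the first row needs stratification or a treatment-by-entry-use interaction.

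**Size of the effect on tolerability.** Let r be the allopurinol event risk in new starters, q the share of the arm already on allopurinol, and k the users' risk relative to starters. Then

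pooled allopurinol risk = r × [(1 − q) + qk],

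a relative reduction of q(1 − k). Febuxostat's risk is taken as the same in both rows, since all of its patients are starters. The documents give neither q nor k. I assume q from 20% to 60% and k from 0 to 0.5. For r, 5% is a ceiling for rash leading to withdrawal (section III says rates were generally well below it), and 1% is the ceiling the same section gives for hypersensitivity syndrome.

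| q | k | Factor | r = 5% becomes | r = 1% becomes | Starter risk ratio hidden by pooled parity |
|---|---|---|---|---|---|
| 20% | 0.5 | 0.90 | 4.5% | 0.90% | 1/0.90 = 1.11 |
| 40% | 0.25 | 0.70 | 3.5% | 0.70% | 1/0.70 = 1.43 |
| 60% | 0 | 0.40 | 2.0% | 0.40% | 1/0.40 = 2.50 |

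If k = 1 there is no distortion.

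**Hypersensitivity syndrome in counts.** With 950/2 = 475 per arm, 1% is 4.75 expected events at most. Suppose a share f of the arm is past six months of use and only the remaining tenth of the risk applies to them. The factor is then 1 − 0.9f: 0.73, 0.55 and 0.46 for assumed f of 30%, 50% and 60%. In counts that is 3.5, 2.6 and 2.2 events instead of 4.75, a shift of at most about 2.6 events.

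**Phase 1 flares.** Section X treats allopurinol 300 mg and febuxostat 40 mg as similar in urate lowering. Assuming also that the effect is linear in dose, the first change in allopurinol-equivalent mg is:

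| At entry | Allopurinol arm | Febuxostat arm | Gap |
|---|---|---|---|
| No allopurinol | 100 | 300 | 200 |
| 100 mg | 0 | 200 | 200 |
| 200 mg | 0 | 100 | 100 |
| 300 mg | 0 | 0 | 0 |

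The gap between arms is never larger in users than in starters.

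**The case against.** The strongest reply has four parts.

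- **The mixture is intended.** Section IX openly enrolls patients uncontrolled on allopurinol up to 300 mg, so escalate-versus-switch is part of the trial's question, and the pooled randomized contrast is valid for the population enrolled. This stands. The difficulty arises only when the pooled result is carried over to patients starting therapy.
- **Tolerance was shown only at low dose.** Users are then titrated up to a possible 800 mg/day, and section III reports that adverse reactions in CKD followed the rate of dose increase. This also stands. It means k could be well above the values assumed here.
- **The analyses are exploratory and may be adjusted.** The SAP labels all secondary analyses as descriptive and exploratory and runs them with and without covariates. Protocol section VIII lets analyses 2 to 7 adjust for baseline covariates. This lowers the stakes, but entry allopurinol use is not named among the covariates, and main-effect adjustment would not isolate starters.
- **The events are few.** For hypersensitivity syndrome this is right, as the counts show. The point matters more for rash and adverse-event withdrawal, although the six-month figure cannot be applied to them.

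A reader might go further and infer that allopurinol will also look better on Phase 1 flares. The documents do not support a direction: on their own dose comparison, pooling users leaves the between-arm gap unchanged or dilutes it, and all participants receive prophylaxis. A reader might also infer that the trial cannot speak to starting either drug. It can, because first-time patients are randomized and the SAP balances on entry use. The plan simply does not ask for the result.

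**Conclusion.** The point holds for tolerability. Only the allopurinol arm can contain patients established on their assigned drug, and no planned analysis separates them. The direction follows from the protocol's own facts: intolerant patients are excluded, and hypersensitivity is concentrated early in treatment. The pooled comparison would therefore tend to understate early allopurinol intolerance in new starters.

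The size cannot be fixed. The 10% to 60% relative reduction rests on assumed values of q and k. Even the share of users would not give f, since section X requires ongoing use but no minimum duration. The site survey in protocol Table 7 does not settle it either. At the 17 sites giving plain numbers in both columns, 6,509 first-time prescriptions against 23,520 for allopurinol at up to 300 mg is 28%, but that is a screening pool that includes patients already at target.

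For Phase 1 flares, two contrasts are mixed and no direction is established. The primary Phase 3 comparison and its power are not shown to be affected. This is a worthwhile, inexpensive improvement to secondary analyses and does not threaten the trial's main conclusion.

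**What to change.** In SAP 5.5, objectives 1(b), 6 and 7:

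- Report rash, protocol-defined hypersensitivity, withdrawal for adverse events, and Phase 1 and Phase 2 flare counts by arm within strata of allopurinol use at entry, alongside the pooled result.
- Add a treatment-by-entry-use interaction where counts allow.
- State that any conclusion about starting therapy rests on participants not taking allopurinol at entry.

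Reconcile the balancing factor first. Earlier receipt of any urate-lowering therapy (protocol section VI) and current allopurinol use (SAP 5.2) classify former allopurinol users and uricosuric users differently, and the strata depend on which definition was recorded.

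The cost is a few tables from data already collected, with wider intervals in each stratum. Hypersensitivity in CKD 3 will be very sparse: about 317/2 = 158.5 patients per arm at 1% gives at most 1.6 expected events per arm before any split. In that subset, list the cases and do not test them.

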**CSP 594**  
**Comparative Effectiveness in Gout:**  
**Allopurinol vs. Febuxostat**

**Statistical Analysis Plan**

## Abbreviations

ACR = American College of Rheumatology  
AE = Adverse Event  
AHS = Allopurinol Hypersensitivity Syndrome  
CKD = Chronic Kidney Disease  
CRF = Case Report Forms  
CSP = Cooperative Studies Program  
eGFR = estimated Glomerular Filtration Rate  
RAIN = Rheumatology and Arthritis Investigational Network  
SAE = Serious Adverse Event  
sUA = serum Uric Acid  
SAP = Statistical Analysis Plan  
ULT = Urate Lowering Therapy

## 1. Introduction

This document outlines the statistical methods for the analysis of data collected in the Department of Veterans Affairs Cooperative Studies Programs (CSP) study #594 entitled “Comparative Effectiveness in Gout: Allopurinol vs Febuxostat”. The purpose of this document is to provide guidelines from which the analysis will proceed. Deviations from these guidelines will be documented and filed electronically in the study central file SharePoint site.

The following documents were used in preparation of this statistical analysis plan (SAP):

- Clinical Study Protocol CSP #594
- Case Report Forms (CRF) from above entitled Protocol
- Global CSP SOP 2.9: “Developing and Conducting Statistical Analyses”
- Local Work Instruction WI 201 Statistical Analysis Plan and Biostatistical Research Data Processing Plan Creation and Amendment
- Local Job Aid No. 036: Guide to Writing Statistical Analysis Plans

## 2. Overview of the Study Design and Objectives

The proposed study is a double-blinded, two-arm intervention trial testing whether appropriately titrated allopurinol is non-inferior to appropriately titrated febuxostat.

Participants will be recruited from 19 Veteran Affairs and 5 RAIN sites. Individuals with a history of gout who continue to be hyperuricemic (sUA  $\geq$  6.8mg/dl) and fulfill entry criteria will be invited to participate. A total of 950 participants will be randomized in a 1:1 ratio to receive either allopurinol or febuxostat. Recruitment will occur over 24 months. The total duration of the trial will be 4 years.

Participants will be followed for 72 weeks: a 24-week Dose Titration Phase (Phase 1) followed by a 24-week Maintenance and Optimization Phase (Phase 2) and then a 24-week Steady State Flare Observation Phase (Phase 3). Patients will undergo active surveillance during Phases 1 and 2 with scheduled in-person study visits, while Phase 3 observation will be conducted remotely using telephone encounters. There will be one study visit at week 60 to return bottles and diaries and pick up a new three-month supply of study medication.

The primary objective:

To compare the efficacy of appropriately titrated doses of two ULTs, allopurinol and febuxostat, in reducing gout flares during Phase 3, weeks 49-72, in participants with gout who are hyperuricemic prior to study entry.

Secondary Objective:

- 1) To compare the efficacy and tolerability of allopurinol and febuxostat in reducing gout flares among participants with gout who have stage 3 chronic kidney disease (CKD 3) and are hyperuricemic at baseline.
- 2) To compare the efficacy of the two ULT dosing regimens in achieving sUA < 6.0 mg/dL between weeks 36 and 48 (i.e., during Phases 1 and 2: the dose titration phase, and the dose maintenance and optimization phase).
- 3) To determine if the number of gout flares in phase 3 in participants who achieve a sUA < 6.0 mg/dl by 48 weeks differ compared with those who do not, regardless of treatment assignment.
- 4) To determine whether health-related quality of life measures differ between participants randomized to allopurinol compared to febuxostat and differ by achievement of sUA < 6.0 mg/dL, regardless of treatment assignment.
- 5) To determine whether change in tophi area differ by location between participants randomized to allopurinol compared to febuxostat, and between participants who achieve or do not achieve sUA < 6.0 mg/dL, regardless of treatment assignment.
- 6) To determine whether the number of gout flares during each of the trial's 3 phases differ between participants randomized to allopurinol compared with febuxostat and then extend this analysis to the entire 72-week period.
- 7) To explore the tolerability/toxicity of the two ULT dosing regimens.

8) To describe the effects of baseline covariates and time-dependent covariates on the primary results.

